6.2.5.2. ADA Titer

For patients who are ADA ever positive, the maximum observed ADA titer for a patient will be summarized, overall and by ADA subcategories (baseline ADA positive, treatment-boosted ADA, treatment-induced ADA, transient ADA response, persistent ADA response) of patients having each discrete maximum titer value will be tabulated. The denominator to calculate the percentages will be the total number of patients in the associated ADA subcategory.

For patients with treatment-induced ADA, a cross tabulation of duration of ADA response and maximum ADA titer will be provided. The following categories for duration of ADA response will be used: ≤ 1 , >1 to ≤ 3 , >3 to ≤ 5 , >5 to ≤ 7 , >7 to ≤ 13 , >13 to ≤ 16 , >16 to ≤ 25 , >25 weeks. In this categorization, the censoring in duration of ADA response is ignored.

6.2.5.3. Analysis of PK, Safety and Efficacy by Immunogenicity Status

The following ADA and nAb status will be used for the analyses described below.

ADA

- ADA ever-positive versus ADA never-positive;
- ADA: treatment-induced ADA versus ADA never-positive or baseline ADA positive.

nAb

- nAb ever-positive versus nAb never-positive;
- nAb: treatment-induced nAb versus nAb never-positive or baseline nAb positive.

Data listings will include immunogenicity data together with relevant PK, safety and efficacy data.

PK parameters and immunogenicity status

The following analyses will include patients in both the immunogenicity analysis set and in the PK parameter analysis set. The PK endpoints pertinent to the immunogenicity analyses are C_{trough} and C_{max} .

Blood samples for avelumab PK will be collected as outlined in the “Schedule for Pharmacokinetic Sample Collection” table of the Schedule of Assessments section of the protocol.

C_{trough} and C_{max} will be summarized descriptively (n, mean, SD, CV, median, minimum, maximum, geometric mean, its associated CV, and 95% CI) by nominal time and ADA status. Linear-linear plots of mean and median for C_{trough} and C_{max} over nominal time and by ADA status will be presented.

Among patients with treatment-induced ADA, analyses will be conducted to assess whether C_{trough} and C_{max} have any changes before and after the first positive ADA assessment. To be included in this analysis, patients must have the same PK parameter available both before and after the first positive ADA assessment. Relative PK day will be calculated as:

$$(\text{PK assessment nominal day}) - (\text{first positive ADA assessment nominal day}).$$

Nominal day is the protocol scheduled timing for an assessment. For example, if C_{trough} is collected on Day 1 of Cycle 2 and the first positive ADA result is observed on Day 1 of Cycle 3, then the relative PK day for this C_{trough} is -14. Linear-linear plots of mean and median for C_{trough} and C_{max} over relative PK day will be presented.

As data permit, the analyses described above will be repeated for nAb.

Safety and immunogenicity status

The following analyses will include patients in the immunogenicity analysis set.

The frequency (number and percentage) of patients with each of the following will be presented by ADA status.

- TEAEs, by SOC and PT;
- TEAEs leading to dose reduction of avelumab, by SOC and PT;

- TEAEs leading to discontinuation of avelumab, by SOC and PT;
- TEAEs leading to discontinuation of study treatment by SOC and PT;
- Grade ≥ 3 TEAEs, by SOC and PT;
- SAEs, by SOC and PT;
- IRRs, by PT.

For patients who had at least one IRR and have treatment-induced ADA, time related to first onset of an IRR (infusion 1, infusion 2, infusion 3, infusion 4 or later) will be summarized taking into account whether the IRR occurred on or after the first ADA positive assessment or whether the IRR occurred before the first ADA positive assessment.

As data permit, the analyses described above will be repeated for nAb.

Efficacy and immunogenicity status

For the ADA ever-positive patients, a listing will be prepared with patient ID, start and stop of avelumab treatment, date of first positive ADA result, time to ADA response, duration of ADA response, date of last ADA positive result, BOR, DR, PFS time or censoring time and reason for censoring, and OS time or censoring time and reason for censoring. If applicable, date of first positive nAb result, time to nAb response, duration of nAb response, date of last nAb positive result will also be presented.

For the ADA ever-positive patients, the percent change from baseline in target lesions as well as the first occurrence of a new lesion and patient off avelumab treatment will be displayed against time point (weeks) in a line plot. Additional symbols will indicate the first and last ADA positive result and, if applicable, the first and last nAb positive result.

CCI [REDACTED]

[REDACTED]

[REDACTED]

[REDACTED]

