29. Pharmacokinetics for axitinib: PK samples for axitinib (3 mL) will be collected at pre-dose and 2 hours post-dose on Day 1 of Cycle 1, Cycle 2 and Cycle 3. Details are outlined in Section 7.1.5.
30. Pharmacokinetics for avelumab: Blood samples (3.5 mL) for avelumab PK will be collected in all patients: pre-dose and at the end of infusion (immediately before the end of avelumab infusion) on Day 1 of Cycle 1, 2, 3 and 4. After that, trough (pre-dose) samples will be collected at cycles 6 and 8 and then every 4 cycles, ie., every 8 weeks thereafter. Pre-dose samples can be taken up to 2 hours prior to the start of avelumab infusion. Details are outlined in Section 7.1.5.
CCI [Redacted]

32. **Mandatory Archival or *de novo* FFPE Tumor Tissue:** CCI [REDACTED]
[REDACTED] The biopsy sample(s) should be formalin-fixed and paraffin-embedded and the resulting FFPE tissue block(s) should be submitted to the Central Laboratory. CCI [REDACTED]
[REDACTED] or *de novo* tumor tissue from cytologic sampling (eg, fine needle aspiration, including FFPE cell pellet material) is not adequate and should not be submitted. See Section 6.1.1 and Section 7.4.1.
33. **Anti-Avelumab Antibodies (Anti-Drug Antibodies, ADAs) and Neutralizing Antibodies (nAb):** One blood sample (3.5 mL) for anti-avelumab antibodies will be collected pre-dose on Day 1 of Cycle 1, 2, 3, 4, 6, and 8 and then every 4 cycles, ie., every 8 weeks thereafter. All samples should be drawn within 2 hours before start of avelumab infusion. All the samples that are positive for ADA may also undergo characterization for nAb. ADA sample at 30 day follow up is collected at 30 days after end of treatment of avelumab regardless of continuation of axitinib therapy. See Section 7.3.

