5.2.7. Definition of On-treatment Period

Safety endpoints will be summarized based on the on-treatment period unless otherwise specified.

On-treatment period is defined as the time from the first dose of study treatment through minimum (30 days + last dose of study treatment, start day of new anti-cancer drug therapy – 1 day).

Safety data collected outside the on-treatment period as described above will be listed and flagged in listings but not summarized.

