6.2.5. Endpoints for Immunogenicity Data of Avelumab

Blood samples for avelumab immunogenicity testing will be collected pre-dose on Cycle 1, 2, 3, 4, 6 and 8. Subsequently, testing should be performed approximately every 8 weeks. All samples should be drawn within 2 hours before start of avelumab infusion. Additional samples for anti-avelumab antibodies (and simultaneous PK draws for measurement of avelumab) will be collected at the Day 30 Follow-up visit after the end of avelumab treatment.

Samples positive for ADA will be analyzed for titer and may be analyzed for nAb. As of the finalization of this SAP, the nAb assay is not yet available, therefore the analyses of nAb data described in the following sections will only be conducted contingent upon assay and data availability at the time of reporting.

Patients will be characterized into different ADA categories based on the criteria defined in [Table 9](#).

Table 9 Patients Characterized Based on Anti-Drug Antibody Results (ADA Status)

Category	Definition	Subjects at Risk (Denominator for Incidence)
ADA never-positive	No positive ADA results at any time point; ADA-negative patients (titer < cutpoint)	Number of patients with at least one valid ADA result at any time point
ADA ever-positive	At least one positive ADA result at any time point; ADA-positive patients (titer ≥ cutpoint)	Number of patients with at least one valid ADA result at any time point
Baseline ADA positive	A positive ADA result at baseline	Number of patients with valid baseline ADA result
Treatment-boosted ADA	A positive ADA result at baseline and the titer ≥8×baseline titer at least once after treatment with avelumab	Number of patients with valid baseline ADA results and at least one valid post-baseline ADA result
Treatment-induced ADA	Patient is ADA-negative at baseline and has at least one positive post-baseline ADA result; or if patient does not have a baseline sample, the patient has at least one positive past-baseline ADA result	Number of patients with at least one valid post-baseline ADA result and without positive baseline ADA result (including missing, NR)
Transient ADA response	If patients with treatment-induced ADA have (a single positive ADA result or duration between first and last positive result <16 weeks) and ADA result at the last assessment is not positive.	Number of patients with at least one valid post-baseline ADA result and without positive baseline ADA result (including missing, NR)

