6.5.3. Study Treatment Compliance and Exposure

The following analyses will be based on the safety analysis set by treatment group.

Cycle definitions for study drugs that are administered in combination apply to all the study drugs in the combination. Ie, cycle is patient-dependent, rather than study-drug-dependent when study drugs are administered in combination.

For Cycle X, actual cycle start date for each patient is:

- the earliest start date of dosing in the Cycle X Day 1 visit eCRF exposure page, if the patient received study treatment on that visit (ie, any study drug with dose >0 at that visit);

- the first day of assessments in the Cycle X Day 1 visit, if the patient did not receive study treatment on that visit (ie, all study drugs had dose=0 at that visit). Use start date in the exposure page if available; if start date is not available then use date of collection of vital signs on Cycle X Day 1 visit.

Actual cycle end date for each patient is,

- for all cycles X except the last cycle, actual cycle end date = actual cycle (X+1) start date – 1 day;
- for the last cycle, actual cycle end date = actual cycle start date + intended cycle duration (in days) – 1 day.

Cycle duration (weeks) = (actual cycle end date – actual cycle start date + 1)/7

When summarizing exposure for each study drug, only cycles from first dose of study treatment until the last cycle with non-zero dose of at least one of the study drugs should be included.

Exposure may be summarized (per cycle and/or overall) as dose received (cumulative dose, actual dose intensity) and as dose received relative to intended dose (relative dose intensity [RDI]).

The information that will be summarized depends on how the study drug is dosed (eg, infusion cyclical, oral daily, oral cyclical).

The formulae below should be applied to each study drug separately even when study drugs are administered in combination.

The derivations below are provided assuming 1 cycle = 2 weeks and for the following study drugs (administered alone or in combination):

- Avelumab administered as a 1-hour IV infusion at a dose of 10 mg/kg once every 2 weeks in 2-week cycles.
- Axitinib administered orally BID PO at a dose of 5 mg.

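### AE percentages by ADA status (SAP 6.2.5.3) ignore when the first positive sample occurred, so they can show an association that reflects time on treatment

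*SAP*

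**What the plan says.** SAP 6.2.5, Table 9, defines ever-positive as "At least one positive ADA result at any time point" and never-positive as "No positive ADA results at any time point". Either group needs only one valid ADA result. SAP 6.2.5.3 then sets up two contrasts: "ADA ever-positive versus ADA never-positive", and treatment-induced ADA against never-positive or baseline-positive patients.

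For safety the SAP states "The frequency (number and percentage) of patients with each of the following will be presented by ADA status". The list covers TEAEs, TEAEs leading to avelumab dose reduction, two discontinuation tables, Grade 3 or higher TEAEs, SAEs and IRRs. None of these tables has an exposure adjustment, a landmark or a time-varying status.

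Two clocks run with treatment:
- ADA samples "will be collected pre-dose on Day 1 of Cycle 1, 2, 3, 4, 6, and 8 and then every 4 cycles" (Protocol, note 33 on anti-avelumab antibodies).
- The AE window is "the time from the first dose of study treatment through minimum (30 days + last dose of study treatment", cut short only by a new anti-cancer drug (SAP 5.2.7).

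The SAP does use the date of the first positive result in two other places in 6.2.5.3. Time to first IRR is summarized "taking into account whether the IRR occurred on or after the first ADA positive assessment", and trough and maximum concentrations are compared before and after the first positive result.

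**The concern.** Group membership is decided by what happens later. A patient with an SAE in week 3 and a first positive sample in week 30 is counted as an ADA-positive patient with an SAE. A patient who stops after a few weeks has had few samples and little AE time, and will tend to appear as never-positive with no event. Longer treatment therefore raises both the chance of a positive sample and the chance of an AE, which is enough to link the two without any biological relation.

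At stake is how the descriptive link between immunogenicity and safety is read. A clinical study report, or a later pooling across avelumab studies, could carry forward an apparent ADA-toxicity relation, or miss a real one, because of treatment duration.

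**Working it through.** **Inputs from the documents.** There are about 20 patients (SAP 5.1.1). Cycles last 2 weeks: "The derivations below are provided assuming 1 cycle = 2 weeks". Scheduled pre-dose samples fall at weeks 0, 2, 4, 6, 10, 14, 22, 30, 38, 46 and so on: 4 by week 8, 7 by week 26 and 10 by week 52. A further sample is taken 30 days after avelumab ends. The AE window runs to last dose plus 30 days. The primary cut-off is 78 weeks after the last patient is treated (SAP 2).

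**The plan's own figure.** The documents give none for the AE-by-ADA tables. The only related one is the sample-size statement: 1 − 0.9^20 = 0.878, which matches the stated 88% after rounding.

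**Assumptions, because the documents give no values for this study.** ADA and AE times are generated independently, with 400,000 simulated patients per scenario and treatment capped at 78 weeks.
- Set A: exponential treatment time with median 13, 26 or 52 weeks; 52-week ADA probability 10% or 25%; 52-week AE probability 20% or 50%.
- Set B: mean treatment 16 to 36 weeks; ADA hazard 0.5 to 2% per week; AE hazard 1 to 3% per week unless stated.

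**Quantity computed.** Risk ratio = P(AE | ever-positive) / P(AE | never-positive). The true value is 1.00.

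| Situation | Set A | Set B |
|---|---|---|
| Gradual ADA onset, AE does not stop treatment | 1.25 to 1.61 | 1.34 to 1.73 |
| Gradual onset, half of AEs stop treatment | 1.04 to 1.27 | not run |
| Gradual onset, every such AE stops treatment | 0.74 to 1.00 | 0.91 to 1.01 |
| All ADA arises in weeks 0 to 6 | 0.98 to 1.01 | 1.00 to 1.04 |
| Gradual onset, AE hazard 10% per week | not run | 1.13 to 1.21 |
| Gradual onset, AE hazard 30% per week | not run | 1.02 to 1.04 |

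**One scenario in full.** With median treatment 26 weeks, ADA 25% and AE 50%, the AE proportions are 48.0% and 33.0%. The ratio is 48.0 / 33.0 = 1.45 and the difference is 15.0 points. Median treatment is 50 weeks in ever-positive and 22 weeks in never-positive patients.

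A hand check uses the AE hazard ln 2 / 52 = 0.0133 per week and a window of treatment plus 30/7 = 4.3 weeks:
- at 22 weeks: 1 − exp(−0.0133 × 26.3) = 29.6%;
- at 50 weeks: 1 − exp(−0.0133 × 54.3) = 51.5%.

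The gap comes from duration alone. The simulated figures are closer together because they average over the spread of durations.

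**Misplaced events.** In the first row of the table, 54 to 62% (set A) and 52 to 67% (set B) of the AEs counted under ever-positive came before the first positive sample.

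**Effect of respecting timing.** When time and events before the first positive sample are counted as ADA-negative and events are divided by patient-time, the rate ratio is 0.96 to 1.03 (set A) and 0.99 to 1.02 (set B). The artefact disappears.

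**Noise at the actual size.** With 20 patients, mean treatment 24 weeks, ADA hazard 1% and AE hazard 2% per week, about 4 patients are ever-positive. The ever-minus-never difference averages +16 points, with a 95% simulation range of −41 to +72, and it is negative in 26% of simulated trials.

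**The case against.** The tables are plain counts. SAP 5.1.1 plans no hypothesis test and SAP 5.1.2 has no decision rules. With perhaps 1 to 5 ever-positive patients, random error probably exceeds the bias. Table 9 states openly that status covers any time point, and patients positive at baseline have no pre-positive time at all. SAP 6.2.5.3 also promises listings that show immunogenicity beside safety data, so in a study of this size a reader could check timing patient by patient. All of this stands, and it limits the weight of the point. It does not remove it: percentages are what gets quoted, and a bias built into a table does not shrink when tables are pooled.

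Several stronger readings are tempting, and the documents do not support them.
- A reader might infer that the SAP treats ADA status as known at baseline. It does not say so; the tabulation merely has that effect.
- A reader might infer that timing is recognised only for IRRs. The before-and-after PK comparison shows otherwise. For efficacy, 6.2.5.3 plans a listing and a plot of ever-positive patients, not a crude ever/never comparison.
- A reader might infer that the immunogenicity objective is misstated. Its endpoint is the ADA and nAb categories of Tables 9 and 10, which these AE tables cannot change.

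**Conclusion.** The point holds as a conditional one. The AE-by-ADA percentages in SAP 6.2.5.3 can show a spurious association, because status is set by later samples and exposure is not accounted for. A reader might infer that a false excess of toxicity will appear, but the documents do not establish that. The excess (risk ratio about 1.25 to 1.7) needs gradual ADA onset and AEs that are not very common and seldom end treatment. With early onset or very common AEs the ratio is near 1.0. For AEs that always end treatment, as in the two discontinuation tables, it is about 0.74 to 1.0, so any bias there runs the other way.

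These sizes depend on assumed ADA incidence and onset, AE rates and treatment duration. The tables are descriptive, and the primary endpoint and ADA incidence are untouched. This is an inexpensive improvement to secondary displays, not a flaw in the trial's main analysis.

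**What to change.** Amend the safety part of SAP 6.2.5.3 as follows.
1. For patients with treatment-induced ADA, split the AEs in each category into onset before and onset on or after the first positive result, as is already done for IRRs.
2. Show treatment duration by ADA status beside these tables.
3. At the overall-category level only, not by SOC and PT, report events per patient-time with pre-positive time counted as ADA-negative. State where baseline-positive patients are placed, since they have no pre-positive time.
4. Keep the ever/never percentages, with a footnote that they are not adjusted for exposure or for the timing of the first positive result.

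The date of the first positive result is already derived for time to ADA response (SAP 6.2.5.1), so the cost is SAP wording and some table programming. The downside is a few more columns, many of them sparse. The split is also at detection rather than true onset: after Cycle 8 samples are 4 cycles × 2 weeks = 8 weeks apart, so some events just before the first positive sample will be placed imprecisely.

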6.4. Subset Analyses

Subset analyses using PD-L1 status (thresholds are $<1\%/ \geq 1\%$ and $<10\%/ \geq 10\%$) at baseline will be performed for OR and PFS per investigator assessment and BICR assessment based on RECIST v1.1 CCI [REDACTED], and for OS, based on the FAS.

6.5. Baseline and Other Summaries and Analyses

6.5.1. Baseline Summaries

The following analyses will be based on the FAS overall and separately by treatment group. Demographic characteristics except for physical measurements (see [Section 6.5.1.1](#)), significant medical history (see [Section 6.5.1.2](#)) and disease characteristics (Barcelona Clinic Liver Cancer [BCLC], vascular invasion, extrahepatic spread, intrahepatic tumor, extrahepatic spread and intrahepatic tumor and baseline AFP level; see [Section 6.5.1.3](#)) will be also summarized by PD-L1 status at baseline based on the FAS.

6.5.1.1. Demographic Characteristics

Demographic characteristics and physical measurements will be summarized by treatment group using the following information from the ‘Screening/Baseline Visit’ eCRF pages.

- Demographic characteristics:
 - Gender: Male, Female;
 - Race: White, Black or African American, Asian, American Indian or Alaska Native, Native Hawaiian or other Pacific Islander, Multiracial, Not Reported;
 - Racial Designation: Japanese, Korean, Chinese, Other;
 - Ethnic origin: Hispanic/Latino (Yes/No), Not Reported;
 - Age (years): summary statistics;
 - Age categories:
 - <65 years, ≥65 years;
 - <65, 65-<75, 75-<85, ≥85 years;
 - Eastern Cooperative Oncology Group (ECOG) Performance Status: 0, 1, 2, 3, and 4.
- Physical measurements:
 - Height (cm);
 - Weight (kg);
 - Body Mass Index (BMI) (kg/m²).
- Child-Pugh score:
 - Child-Pugh score (summarized as qualitative variable).

The listing of demographics and baseline characteristics will include the following information: patient identifier, treatment group, age, sex, race, ethnicity, height (cm), weight (kg), BMI (kg/m²), ECOG performance status, and Child-Pugh score.

6.5.1.2. Medical History

- Medical history

Medical history will be coded using the most current available version of Medical Dictionary for Regulatory Activities (MedDRA) and will be summarized from the ‘Medical History’ eCRF page. Medical history will be summarized as the numbers and percentages of patients by MedDRA preferred term (PT) as event category and MedDRA primary system organ class (SOC) as summary category. Each patient will be counted only once within each PT or SOC.

Medical history will be displayed in terms of frequency tables: ordered by primary SOC and PT in alphabetical order.

- Significant medical history

Significant medical history will be summarized by treatment group using the following information from the ‘Significant Medical History’ eCRF pages.

- Hepatitis B: Yes, No
- Hepatitis C: Yes, No
- Alcoholic hepatitis: Yes, No
- Non-alcoholic steatohepatitis: Yes, No

6.5.1.3. Disease Characteristics

Information on disease characteristics collected on ‘Primary Diagnosis’, ‘Subject Stratification’, ‘Substance Use’, ‘RECIST’ and ‘Laboratory Data’ eCRF pages will be summarized overall and by treatment group. Summary statistics will be presented for the following.

From the ‘Primary Diagnosis’ eCRF page:

- Primary diagnosis (summarize all categories collected in the ‘Primary Diagnosis’ eCRF page);
- Method of primary diagnosis: Histology, Cytology, Non-invasive;
- BCLC: A, B, C, D, Unknown;
- Histopathological grade: Grade 1, 2, 3, 4;
- TNM current stage: Stage I, Stage II, Stage IIIA, Stage IIIB, Stage IIIC, Stage IVA, Stage IVB, Unknown;

- Time since initial diagnosis to date of first dose of study treatment (months), defined as (date of first dose of study treatment – date of initial diagnosis)/30.4375;
- Time since histopathological diagnosis to first dose of study treatment (months), defined as (date of first dose of study treatment – date of histopathological diagnosis)/30.4375;
- Time since recurrence/metastatic of disease to first dose of study treatment (months), defined as (date of first dose of study treatment – date of recurrence/metastatic of disease)/30.4375;
- Time since diagnosis of local/regional recurrence of disease (months), defined as (date of first dose of study treatment – date of diagnosis of local/regional recurrence of disease)/30.4375.

From the Subject Stratification eCRF page:

- Vascular invasion: Yes, No;
- Extrahepatic spread: Yes, No;
- Intrahepatic tumor: Yes, No;
- Extrahepatic spread and intrahepatic tumor: Both, Extrahepatic spread only, Intrahepatic tumor only, None.

From the RECIST eCRF page:

- Measurable disease (lesions) at baseline (Yes, No);
- Involved tumor sites at baseline.

From Laboratory page:

- Baseline AFP <100 ng/mL, ≥100 - <200 ng/mL, ≥200 - <400 ng/mL, ≥400 ng/mL;
- Number of patients who was diagnosed by imaging method by AFP level <400 ng/mL, ≥400 ng/mL.

From the 'Substance Use' eCRF page:

- Smoking history:
 - Never smoker vs current vs former smoker;
 - Smoking exposure (pack-years): 0, <20, 20-<40, ≥40 and summary statistics;

- Years since quitting: never smoker, current smoker, <5, 5-<10, ≥10 and summary statistics.

Specifications for computation:

- Cigarette equivalents are calculated as follows: one cigar is regarded equivalent to 5 cigarettes and 1 pipe is regarded equivalent to 3 cigarettes.
- Duration of nicotine consumption [years]:
 $(\text{end of nicotine consumption} - \text{start of nicotine consumption} + 1) / 365.25$.
- Pack-years:
 - calculate cigarette equivalents per day using the conversion factors given above;
 - convert to packs per day where 20 cigarettes are regarded as 1 pack;
 - pack-years = packs per day × duration of nicotine consumption [years].

Listing of disease history will be provided with all relevant data (as collected on the ‘Primary Diagnosis’, ‘Subject Stratification’, ‘Substance Use’, ‘RECIST’ and ‘Laboratory Data’ eCRF pages) and derived variables as above.

